Study Number:	GCO#1: 16-1314

A minimum of 3 and a maximum of 6 subjects within a dose level must be observed for one cycle (90 day post EBRT completion) before accrual to the next higher dose level may begin.

Three patients within a dose level must be observed for one cycle (30 days post EBRT) before accrual to the next higher dose level may begin. The treatment for this study is RP + Civasheet implant + adjuvant EBRT for patients with high-risk or intermediate (non-clinically localized) prostate cancer with adverse pathologic features including seminal vesicle invasion, extra prostatic extension or a positive surgical margin. Since the clinical guidelines recommend adjuvant EBRT post RP only for patients with adverse pathologic features at RP, patients without these adverse pathologic features at RP will be replaced with additional patients at that dose level. Since however eligibility criteria is for high risk or non-clinically localized intermediate risk prostate cancer, the anticipated number of patients without these adverse pathologic features who will not receive adjuvant EBRT is 2 or less. While toxicities among these patients will be monitored according to the protocol, toxicities among these patients will not be used in determinations of the MTD. The MTD will only be determined for patients undergoing RP + Civasheet implant + adjuvant EBRT.

If a subject is withdrawn from the study prior to completing the entire cycle of therapy or prior to completing the entire DLT window without experiencing a DLT prior to withdrawal, an additional subject may be added to that dose level. Subjects missing doses due to a DLT will not be replaced since these subjects will be considered to have experienced a dose limiting toxicity.

d) Study Timelines:

The duration of an individual subject's participation in this study including follow-up is 5 years.

The expected duration for the investigators to complete this ranges between 1 month for a minimum of 1 subject and 44 months for a maximum of 12 subjects.

Table 1. Time and events table for those undergoing RP + Civasheet implant + adjuvant EBRT.

[Type here]

Effective Date: 10/18/2022

End Date: 10/17/2023

Protocol Title:	A Phase I Single-Arm Open Label Dose-Escalation Study of CivaSheet with Radical Prostatectomy with or without Adjuvant External Beam Radiation Therapy in Patients with High Risk Prostate Cancer									
Principal Investigator Name/Contact Info:	[name]/ [contact]/ [contact]									

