Primary Contact Name/Contact Info	[contact] [name]									
Date Revised:	7/22/2022									
Study Number:	GCO#1: 16-1314									

	Pre-study	Day 1	Discharge (Typically Day 2)	1 Week	1 Month	6 Weeks	12 Weeks	23 Weeks	35 Weeks	Routinely for 4 years after Study completion
Assessment	X	X	X	X	X	X	X	X	X	X
Informed Consent, AE, Medical History/Medication s, Eligibility criteria, Pre-Surgical clearance (i.e., chest, EKG, etc.).	X									
Toxicity/ AE/ Complications (including DLT) Evaluations		X	X	X	X	X	X	X	X	X
X-Ray	X									
CBC	X	X	X							
Other required labs (PSA, testosterone, BMP)	X	X	X	X			X	X	X	
IIEF	X			X	X			X	X	X
MRI	X									
CT Scan			X		X		X		X	
Radical Prostatectomy + Civasheet Implant		X								
EBRT for 5 weeks						X				

Table 2. Time and events table for those undergoing RP + Civasheet implant without adjuvant EBRT.

	Pre-	Day	Discha	1	1	Routinel

[Type here]

Effective Date: 10/18/2022

End Date: 10/17/2023

Protocol Title:	A Phase I Single-Arm Open Label Dose-Escalation Study of CivaSheet with Radical Prostatectomy with or without Adjuvant External Beam Radiation Therapy in Patients with High Risk Prostate Cancer					
Principal Investigator Name/Contact Info:	[name]/ [contact]/ [contact]					
Primary Contact Name/Contact Info	[contact] [name]					
Date Revised:	7/22/2022					
Study Number:	GCO#1: 16-1314					

	study	1	age (Typically Day 2)	Week	Month	Year for 4 years after Study completion
Assessment	X	X	X	X	X	X
Informed Consent, AE, Medical History/Medication s, Eligibility criteria, Pre-Surgical clearance (i.e., chest, EKG, etc.).	X					
Toxicity/ AE/ Complications (including DLT) Evaluations		X	X	X	X	X
X-Ray	X					
CBC	X	X	X			
Other required labs (PSA, testosterone, BMP)	X	X	X	X		X
IIEF	X			X	X	X
MRI	X					
CT Scan			X		X	
Radical Prostatectomy + Civasheet Implant		X				

Assessments performed exclusively to determine eligibility for this study will be done only after obtaining informed consent. Assessments performed for clinical indications (not exclusively to determine study eligibility) may be used for baseline values even if the studies were done before informed consent was obtained.

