A Phase I Single-Arm Open Label Dose-Escalation Study of CivaSheet With Radical Prostatectomy With or Without Adjuvant External Beam Radiation Therapy in Patients With High Risk Prostate Cancer

[name]

NCT03657108

Document Date: 10-18-2022

**Primary Outcome:** We will determine the MTD for Civasheet when administered with RP and adjuvant EBRT. MTD is defined as the highest dose of the Civasheet® not yielding unacceptable toxicity. Specifically if > 33 % of subjects experience DLT at any dose level, the dose level below that level will be considered the MTD. Or if the highest level (75 Gy) has been reached and < 33% of subjects have experienced DLT, 75 Gy will be considered the MTD.. The present study defines dose limiting toxicity as the development of Grade 3 or higher (According to the NCI'S CTCAE v 4.0) urinary retention, hematuria or rectal bleeding/radiation proctitis within 90 days post EBRT which is given 6 weeks after RP + Civasheet implant for 5 weeks. Toxicities experienced among those not receiving adjuvant EBRT will not be used in the determination of the MTD. Binary or categorical outcomes will be described with proportion and 95% confidence intervals and continuous measures will be summarized with mean (SD) or median (IQR), as appropriate.

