considered the MTD. Or if the highest level (75 Gy) has been reached and < 33% of subjects have experienced DLT, 75 Gy will be considered the MTD. If in the first subject treated at 75 Gy, NCI-CTCAE Grade 4 or higher hematuria, prostatitis or fistula formation occur, no additional subjects will be enrolled at 75 Gy and 60 Gy will be considered the MTD.

**Secondary:** We will describe the adverse events, toxicity and complication profile associated with Civasheet overall and at each dose when administered with RP and EBRT and also separately for those not receiving EBRT. Overall and for 60 and 75 Gy, the toxicity and complication profile associated with the Civasheet® will be assessed. Rates for surgical complications and adverse events, acute (< 90 days) and late (18 months days) GU and GI toxicity and adverse events using the NCI-CTCAE v4.0, RTOG Acute Toxicity Scale and Late Radiation Morbidity scales will be assessed. Erectile preservation and total urinary incontinence will be assessed overall and for each dose group once all subjects have completed the 6 month follow-up after EBRT. Peri- and post-operative complications associated with surgery will be assessed and graded using the Clavien-Dindo classification of surgical complications. Erectile preservation rates [IIEF score (erectile component) > 18] will be assessed, continence defined as the use of no pads will also be assessed. Binary or categorical outcomes will be described with proportion and 95% confidence intervals and continuous measures will be summarized with mean (SD) or median (IQR), as appropriate.

BCR defined as a post-prostatectomy serum PSA > 0.2 ng/ml will also be assessed for each subject. To evaluate cancer control, the Kaplan Meier-Method will be used to estimate BCR overall and for each dose group and separately for those receiving vs. not receiving EBRT once all subjects have completed the 6 months follow-up after EBRT or 6 months follow-up after Civasheet implant if no EBRT is given.

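### Complications between implant and EBRT are tabulated by whether EBRT was later given, which they can influence; the SAP should count them by dose in every implanted man

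*SAP*

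**What the plan says.** The SAP, Secondary, describes the adverse event, toxicity and complication profile overall and "at each dose when administered with RP and EBRT and also separately for those not receiving EBRT". The next sentence promises a profile overall and for the two dose levels without naming a population. On surgery it says: "Peri- and post-operative complications associated with surgery will be assessed and graded using the Clavien-Dindo classification", with no split stated.

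For cancer control the SAP takes "BCR defined as a post-prostatectomy serum PSA > 0.2 ng/ml". It plans Kaplan-Meier estimates overall, by dose group, and "separately for those receiving vs. not receiving EBRT once all subjects have completed the 6 months follow-up after EBRT", or 6 months after implant for men without EBRT.

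The timing is in the SAP's Primary Outcome, where toxicity is counted "within 90 days post EBRT which is given 6 weeks after RP + Civasheet implant for 5 weeks". The same section keeps toxicity in men without EBRT out of the MTD decision.

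Protocol section 3(c) gives one reason for no EBRT, the absence of adverse pathology. It says that "patients without these adverse pathologic features at RP will be replaced with additional patients at that dose level", and it expects two or fewer such men. The same section has a second replacement rule. It begins "If a subject is withdrawn from the study prior to completing the entire cycle of therapy", extends to exit before the DLT window closes, and allows another subject to be added if no DLT had occurred. The reasons for leaving treatment are in Withdrawal of Subjects (3(g), repeated as 3(j)). They include investigator discretion for safety, physician judgement, and progression that requires hormonal therapy.

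**The concern.** Every implanted man is exposed to the surgery and the sheet from day 1. Whether he receives EBRT is settled about 6 weeks later. Sorting the events of those 6 weeks by EBRT receipt sorts them by something in their own future that they may help to decide. A man with adverse pathology who has a serious complication, is withdrawn for safety and never starts EBRT leaves the dose-level RP+EBRT summary. He joins a small group otherwise made up of men with favourable pathology. The first summary then looks too good, and the second describes no recognisable population.

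This matters because harm in a man who never reaches EBRT is excluded from the MTD, so the secondary tables are the main place where it shows. Section 3(c) does treat a man who misses doses because of a DLT as having had a DLT, but that covers only the named toxicities. Read literally, the SAP sentence also attaches the dose breakdown to the RP+EBRT men and does not say that the non-EBRT group is shown by dose.

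The BCR split by receipt has the same structure. A man with adverse pathology who progresses before EBRT and goes to hormonal therapy counts on the non-EBRT curve.

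**Working it through.** The plan gives no complication rate, no rate of missed EBRT and no figure for this bias, so there is nothing of its own to reproduce. Steps 1 and 2 rest on the text. Steps 3 to 5 use assumed rates.

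**1. Order of events.** Surgery and implant are on day 1, pathology is reviewed at the 1-week visit, and EBRT starts at 6 weeks and lasts 5 weeks (protocol, Procedures During Treatment; SAP, Primary Outcome). Perioperative complications precede receipt of EBRT. Pathology comes from the specimen removed on day 1, so later complications cannot change it.

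**2. Route from complication to group.** The groups are defined by receipt. The withdrawal section allows exit for safety or physician judgement, and section 3(c) allows replacement. No text says where a man with adverse pathology who missed EBRT is counted.

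**3. Size under assumptions.** Let c be the true rate of serious early complications, s the proportion of men with a complication who miss EBRT, and m the proportion of the others who miss it. The rate seen among men given EBRT is

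c(1 − s) / [c(1 − s) + (1 − c)(1 − m)].

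With c = 10% and m = 10%, the second term of the denominator is 0.90 × 0.90 = 0.81:

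| s | Calculation | Rate shown |
|---|---|---|
| 10% (= m) | 0.090 / 0.900 | 10.0%, no bias |
| 25% | 0.075 / 0.885 | 8.5% |
| 50% | 0.050 / 0.860 | 5.8% |
| 75% | 0.025 / 0.835 | 3.0% |

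If the others never miss EBRT (m = 0), the rows for s = 25, 50 and 75% become 7.7%, 5.3% and 2.7%. With m = 0 and s = 50%, a true 20% appears as 11.1% and a true 30% as 17.6%.

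**4. In counts.** Suppose that at one dose 8 men are implanted and 6 receive EBRT, and that the one serious complication is in a man who did not. The RP+EBRT table shows 0/6 (exact 95% CI 0 to 46%). All implanted men give 1/8 = 12.5% (0.3 to 53%). The event appears as 1/2 in the non-EBRT group. In expectation at c = 10%, two men with favourable pathology plus one man displaced by a complication show (2 × 0.10 + 1)/3 = 40%.

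**5. BCR.** Table 1 of the protocol marks post-operative PSA on day 1, at discharge and at 1 week, then not until 12 weeks. The follow-up text adds PSA at each follow-up visit. A scheduled PSA failure before week 6 would thus come from few draws, so this route is narrower than the one for complications. If EBRT lasts 5 weeks as planned, the analysis trigger implies minimum follow-up from implant of 6 + 5 + 26 = 37 weeks with EBRT and 26 weeks without. That is a difference in follow-up length, which censoring handles.

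**The case against.** The strongest reply is that unselected summaries are already planned. The protocol's safety-monitoring text, before the Adverse Events heading, promises complication and toxicity rates by grade and dose with no EBRT split. The SAP has its own sentence for overall and for each dose. The Clavien-Dindo sentence has no split, and Withdrawal of Subjects promises an intention-to-treat analysis. This stands in part: an all-implanted summary may well be intended. None of these lines defines its denominator, however. In the protocol sentence, the mention of all subjects says when the 6-month follow-up is complete, not who is counted. The profile sentence that does name groups defines them by EBRT.

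It is also fair that the mechanism is inferred. The only stated reason for no EBRT is pathology, so if the plan runs as written, receipt and the pathology decision coincide. The summaries are descriptive and drive no decision. With 6 men, 10.0% against 5.8% is 6 × 0.042 = 0.25 of one event, and the intervals in the example nearly coincide.

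A reader might infer three stronger points that the documents do not support:

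- **That the two BCR curves start from different time origins.** The 6-month wording sets when the analysis is run. No origin is stated, and the definition refers to PSA after prostatectomy.
- **That events are discarded.** Both groups are reported, and withdrawn men stay in follow-up unless they withdraw consent. The events are relocated.
- **That dose-level BCR is confined to men given EBRT.** The overall and dose-group curves carry no such restriction; only the receipt split is affected.

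**Conclusion.** The point holds as a gap in how the secondary summaries are defined. Early complications and sheet toxicity may be classified by later EBRT, which they can prevent, and no sentence guarantees a by-dose count in all implanted men. The dose-level RP+EBRT profile understates early harm if complications make men less likely to receive EBRT, and not otherwise. Under the assumed rates a true 10% would appear as 8.5% to 3.0%. Those rates are illustrations, and the documents do not allow the actual size to be computed. For BCR the problem is limited to the split by receipt. The MTD rule and the dose-group BCR curves are not affected. This is a problem of interpretation in a very small trial, and it is worth correcting because the correction is nearly free.

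**What to change.** Amend the SAP, Secondary, as follows.

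1. Report Clavien-Dindo complications and all toxicity before the first EBRT fraction by dose for every implanted man. For men without EBRT, close this period at a fixed day, for example day 42 (6 × 7), the planned EBRT start. If the existing overall and by-dose sentence is meant to cover all implanted men, say so there.
2. Split by EBRT only the events that occur after EBRT starts.
3. For the BCR split only, form the groups by the pathology decision (adverse features present or absent). State prostatectomy as the time origin for both curves.
4. List the men who were planned for EBRT and did not receive it, with dose and reason.

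The cost is SAP wording and one extra descriptive table. Surgery date, pathology, adverse events, PSA and withdrawal reasons are already collected, so nothing is added for patients.

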Methods to identify potential subjects: All eligible subjects presenting to the PI or a Co-PI with a diagnosis of NCCN high-very high prostate cancer or NCCN intermediate high-risk cancer with preoperative MRI evidence of ECE, SVI or N1 disease are eligible to undergo RP with adjuvant EBRT as their definitive therapy who also meet inclusion will be consented by the PI or a Co-PI. If a potential subject then expresses interest in participating in the study, the physician/surgeon will present the potential subject with an informed consent form. All aspects of the trial will be discussed with interested subjects including the voluntary nature of their participation. Adequate time will be given to the subject to ask questions related to

[Type here]

Effective Date: 10/18/2022

End Date: 10/17/2023

Protocol Title:	A Phase I Single-Arm Open Label Dose-Escalation Study of CivaSheet with Radical Prostatectomy with or without Adjuvant External Beam Radiation Therapy in Patients with High Risk Prostate Cancer
Principal Investigator Name/Contact Info:	[name]/ [contact]/ [contact]
Primary Contact Name/Contact Info	[contact] [name]
Date Revised:	7/22/2022
Study Number:	GCO#1: 16-1314

the conduct of the trial. We will not advertise for this trial. Subjects will be recruited from the clinic.

b) Inclusion and Exclusion Criteria:

- Any subject with NCCN very high or high risk adenocarcinoma of the prostate defined as $\geq T3a$, Gleason score ≥ 8 , or PSA > 20 who is eligible for RP (open or robotic) with adjuvant EBRT as an initial treatment option.
- Any subject with NCCN Intermediate Risk adenocarcinoma of the prostate defined as T2b-T2c, Gleason score 7, or PSA 10-20 who is eligible for RP (open or robotic) with adjuvant EBRT as an initial treatment option and at least one of the following adverse features present in pre-operative imaging: SVI, ECE, N1 disease.
- Subject must have had a pre-operative MRI or must obtain a pre-operative MRI to be eligible for participation in this study.
- Ability to understand and the willingness to sign a written informed consent.

Exclusion Criteria

- Any subject who has undergone prior radiation to the pelvis.
- Subjects presenting with distant metastases.
- On any investigational drug(s), androgen deprivation therapy or therapeutic device(s) within 30 days preceding screening.
- Currently taking immunosuppressants, or with poorly controlled diabetes (HbA1c > 8).

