- Subjects with prior treatment for PCa including BT, RT or hormone therapy.

c) Number of Subjects:

This is a 3+3 dose escalation design study to determine the MTD. This study will use 2 dose levels and 1-6 subjects at each dose level. The first subject enrolled at each dose level (60 and 75 Gy) will be monitored for the entire DLT window (3 months post EBRT completion) with subsequent subjects enrolled either at the same dose (if only 1 of the first 3 subsequent subjects at the given dose experiences DLT) or in the

[Type here]

Protocol Title:	A Phase I Single-Arm Open Label Dose-Escalation Study of CivaSheet with Radical Prostatectomy with or without Adjuvant External Beam Radiation Therapy in Patients with High Risk Prostate Cancer
Principal Investigator Name/Contact Info:	[name]/ [contact]/ [contact]
Primary Contact Name/Contact Info	[contact] [name]
Date Revised:	7/22/2022
Study Number:	GCO#1: 16-1314

next dose level if the preceding dose is deemed acceptable (i.e., < 33% DLT within 90 days post EBRT). If in the first subject, Grade 4-5 hematuria, fistula formation, proctitis or death occurs in the DLT window, the trial will be terminated. The total number of subjects for this single arm 3+3 trial design is therefore a minimum of 1 and a maximum of 12.

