All screening procedures must be performed within 30 days prior to registration unless otherwise stated. The screening procedures include informed consent, obtaining complete medical, surgical and infection history, demographic data, review of subject eligibility criteria, review of previous and concomitant medications, physical exam including height, weight and vital signs (temperature, pulse, respirations, blood pressure), baseline adverse event

Type here]

Protocol Title:	A Phase I Single-Arm Open Label Dose-Escalation Study of CivaSheet with Radical Prostatectomy with or without Adjuvant External Beam Radiation Therapy in Patients with High Risk Prostate Cancer
Principal Investigator Name/Contact Info:	[name]/ [contact]/ [contact]
Primary Contact Name/Contact Info	[contact] [name]
Date Revised:	7/22/2022
Study Number:	GCO#1: 16-1314

identification, complete blood count test, serum chemistries via a comprehensive metabolic pattern (including albumin, creatinine, etc.), an MRI prior to surgery if not already obtained prior to surgery and completion of the international index of erectile function questionnaire.

Procedures During Treatment

Prior to Treatment

- Physical exam, vital signs
- Hematology
- Serum chemistries

Day 1

- Radical Prostatectomy + Civasheet implant
- X-Ray for baseline assessment of Civasheet stability

1 week after RP + Civasheet Implant

- Physical exam, vital signs
- Hematology
- Serum chemistries
- Pathology Review
- JP Drain and Catheter removal

1 Months After RP + Civasheet Implant

- CT Scan for assessment of Civasheet stability, assessment of cancer recurrence and also for EBRT planning among those with adverse pathologic features who will undergo EBRT

3 and 6 Months After RP + Civasheet Implant

- CT Scan for assessment of Civasheet stability and assessment of cancer recurrence among those with adverse pathologic features who will undergo EBRT.

6 weeks after RP+ Civasheet Implant

- EBRT given at 45 Gy in 25 fractions for 5 weeks (Monday- Friday) among those with adverse pathologic features at EBRT.

[Type here]

Protocol Title:	A Phase I Single-Arm Open Label Dose-Escalation Study of CivaSheet with Radical Prostatectomy with or without Adjuvant External Beam Radiation Therapy in Patients with High Risk Prostate Cancer
Principal Investigator Name/Contact Info:	[name]/ [contact]/ [contact]
Primary Contact Name/Contact Info	[contact] [name]
Date Revised:	7/22/2022
Study Number:	GCO#1: 16-1314

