implant, 6 weeks after EBRT, 3 months after EBRT and 6 months after EBRT during the clinic visits, subjects will complete the IIEF to assess baseline erectile function following treatment. Subjects will undergo PSA testing for each follow-up visit. Those without adverse pathologic features not undergoing adjuvant EBRT will complete the IIEF to assess baseline erectile function following treatment and will also undergo PSA testing for each follow-up visit. Also at each follow-up visit or telephone follow up, subjects will be screened for toxicity and complications. The assessments may be done by phone when possible or lab results may be sent by the patient to our EMR if patient has followed up with an outside physician. For all patients, a CT-scan at day 0 (RP+Civasheet implant) will be done for a baseline stability assessment of the Civasheet. For all patients, a one month post-implant CT scan will be done of the pelvis for three purposes. The first purpose will be to perform a post-implant dosimetric analysis of the implanted Civasheet®. The bladder, rectum and any other identifiable structures (small bowel, large bowel or lymph nodes) will be outlined. The delivered dose will be calculated using a dose volume histogram and recorded. The second part of the CT will be to design the post-implant external beam radiation field among those who will undergo adjuvant EBRT. The third part will be to assess the stability of the Civasheet and any changes in position from initial implant. Among those who will undergo adjuvant EBRT, an additional post-implant CT scan at 90 days and 6 months will be done of the pelvis to prove stability of the device/implant method and to assess for cancer recurrence while those not undergoing adjuvant EBRT will not receive this imaging at 90 days and 6 months.

e) Specimen Banking for Future Uses Not Part of This Project:

NA

f) Data Storage, Transmission and Confidentiality:

To ensure data accuracy and completeness, random checks will be done by members of the research team listed in the protocol who are not directly responsible for data collection and entry. Data irregularities and errors will be collected and reported to the . Data collected and stored for current and future research use will include age, gender, [type here]

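### Erectile preservation is defined only by an IIEF erectile score above 18, with no condition on the pre-study score and no stated denominator, so the rate is capped by baseline function

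*SAP*

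**What the plan says.** The definition is in the SAP's paragraph on secondary outcomes: "Erectile preservation rates [IIEF score (erectile component) > 18] will be assessed". The same paragraph gives the timing and grouping: "Erectile preservation and total urinary incontinence will be assessed overall and for each dose group once all subjects have completed the 6 month follow-up", counted from EBRT. The estimator is also given there: "Binary or categorical outcomes will be described with proportion and 95% confidence intervals".

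The protocol collects a score before treatment. Its screening procedures (Section 3d, Study Timelines) include "completion of the international index of erectile function questionnaire", and Tables 1 and 2 both mark the IIEF at the pre-study visit. After treatment, the follow-up text schedules the IIEF at 1 week after implant and at 6 weeks, 3 months and 6 months after EBRT. It describes the purpose of these later questionnaires thus: "subjects will complete the IIEF to assess baseline erectile function following treatment".

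The inclusion and exclusion criteria (Section 3b) cover disease risk, imaging, prior treatment, immunosuppression and diabetes. Candidates must be men "who is eligible for RP (open or robotic) with adjuvant EBRT as an initial treatment option". None of the criteria concerns erectile function.

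**The concern.** Preservation means keeping a function that was present. A cut-off applied to the follow-up score alone measures how many men have function afterwards. That quantity combines how many had function to begin with and how many of those kept it, and only the second part describes the treatment.

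Men at or below 18 before surgery can enrol. If they are in the denominator, they count against preservation although they had no function, by this definition, to lose. A low rate could then be read as harm from surgery and radiation when it partly reflects who was enrolled. The two dose groups are small, sequential and not randomised, so nothing in the design balances their baseline function.

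The protocol also uses the word baseline for questionnaires completed after treatment. This leaves it less clear which score is the reference, so an explicit rule in the SAP is more necessary.

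**Working it through.** The documents give no expected rate, sample size or power for erectile preservation, so there is no planned figure to reproduce. The check compares two ways of computing the rate.

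**Inputs from the documents**
- Cut-off: erectile component > 18 (SAP, Secondary).
- Group size: "This study will use 2 dose levels and 1-6 subjects at each dose level", with a total of "a minimum of 1 and a maximum of 12" (Protocol, Section 3c).

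**Assumptions, because the documents are silent**
- b, the number of men above 18 before surgery, is varied.
- No man at or below 18 before surgery scores above 18 afterwards.

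**Formulas.** Let N be the number of men in the group and x the number above 18 both before and after treatment.
- Plain reading of the SAP: x / N.
- Conditioned on baseline: x / b.
- Since x cannot exceed b, the first rate cannot exceed b / N.

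**Ceiling in one dose group: N = 6, every man with baseline function keeps it (x = b).** Intervals are exact (Clopper-Pearson) 95%.

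| b | Plain reading, x/N | Conditioned, x/b |
|---|---|---|
| 2 | 2/6 = 33% (4 to 78%) | 2/2 = 100% (16 to 100%) |
| 3 | 3/6 = 50% (12 to 88%) | 3/3 = 100% (29 to 100%) |
| 4 | 4/6 = 67% (22 to 96%) | 4/4 = 100% (40 to 100%) |

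**Both doses together: N = 12, half of the men with baseline function keep it (x = b/2).**

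| b | Plain reading, x/N | Conditioned, x/b |
|---|---|---|
| 4 | 2/12 = 17% (2 to 48%) | 2/4 = 50% (7 to 93%) |
| 6 | 3/12 = 25% (5 to 57%) | 3/6 = 50% (12 to 88%) |
| 8 | 4/12 = 33% (10 to 65%) | 4/8 = 50% (16 to 84%) |

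In the second table the retention rate is 50% in every row, yet the plain-reading rate doubles from 17% to 33% as b rises. If every man starts above 18, then b = N and the two rates are equal.

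**Chance imbalance between doses.** Take two independent groups of 6 with the same true share above 18 at baseline, somewhere from 50% to 70% (assumed). By the binomial distribution, the groups differ by two or more such men with probability 34 to 39%, and by three or more with probability 11 to 15%.

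**The case against.** The strongest reply is that the SAP does not say what the concern attributes to it. A reader might infer that the plan expressly puts all subjects in the denominator. It does not: the words about all subjects fix the time of the analysis, and the contrast drawn is between overall and each dose group. The term preservation could itself imply that only men with prior function count, and the pre-study score is available for that purpose. This part stands: the denominator is unstated, and including everyone is the plain reading, not the literal text. It does not remove the problem. No sentence supplies a baseline restriction, and an unstated denominator can be chosen after the data are seen.

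A reader might also infer that the rule will produce a false difference between 60 and 75 Gy. For example, with 60% true retention, 5 of 6 men above 18 at one dose and 2 of 6 at the other, the expected rates are 0.60 × 5/6 = 50% and 0.60 × 2/6 = 20%. The arithmetic is right, but the retention rate and the split are assumed, and a gap of three or more is the less common case. No test or decision rule compares the doses. The planned intervals would not support a claimed difference in any case: 3/6 has an exact interval of 12 to 88%, and 1/6 has 0.4 to 64%, which overlap widely.

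Third, conditioning leaves very few men. With two men above 18 at baseline, 1/2 has an interval of 1 to 99%, and with none the rate is undefined. This stands, and it is the reason for listing individual scores beside the rate.

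Finally, six men per dose is not a firm upper limit. Section 3c replaces men who turn out to need no EBRT, and allows replacement of men who withdraw, so more than six can be implanted at a dose. The tables above are illustrations at N = 6 and N = 12, not bounds.

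**Conclusion.** The point holds as a defect in the definition of a secondary, descriptive outcome. The SAP gives a cut-off without a baseline condition or a denominator. Read plainly, it reports a rate that cannot exceed the share of men above 18 before surgery unless function improves: 33%, 50% or 67% if 2, 3 or 4 of 6 men are. The actual distortion cannot be stated, because the documents give no baseline share; it is nil if every man starts above 18.

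A reader might infer that dose finding is compromised. The documents do not support that: the MTD rests on dose-limiting toxicities alone, and erectile function is not among them. The change should be made because the rate as defined would mislead and the correction is cheap, not because the conduct of the trial depends on it.

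**What to change.** In the SAP's secondary outcomes:

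1. Define erectile preservation as an IIEF erectile component > 18 at the 6-month follow-up after EBRT, among subjects with a score > 18 at the pre-study assessment.
2. For men who receive no EBRT, use 6 months after implant and report them separately. The SAP already uses this time point and this split for biochemical recurrence.
3. Show the number of men above 18 pre-study, overall and by dose. If that number is zero in a group, report no rate for it.
4. List each subject's pre-study and follow-up scores with the change, including men at or below 18 at baseline, so that no one drops out of view.

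**Cost.** A few sentences in the SAP, a smaller denominator and a wider interval. For men who receive EBRT, both scores are already scheduled. For men without EBRT, one point needs confirming: Table 2 marks the IIEF at 1 week, at 1 month and then at routine follow-up, and the follow-up text gives both a six-monthly and a yearly schedule. The protocol should make clear that these men complete the questionnaire at 6 months.
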